### 11.9 Assessment of Efficacy

Incisional hernia rate within 24 months of midline laparotomy as assessed by a CT-scan and a physical examination including a hernia clinical examination will be recorded in the Club Hernie Registry Database and used to assess the efficacy of the ProGrip™ Self- gripping polyester mesh.

## **11.10 Assessment of Safety**

The incidence of AEs related to device and/or procedure will be recorded starting at the time of informed consent signature through the 24 months post-operative follow-up. The data will be analyzed in the Safety Analysis Set. See Section 13 for further information on the collection of AEs and safety information.

## **11.11 Recording Data**

This study will utilize the Club Hernie electronic database. All data requested on the Club Hernie Registry Database are required. Study visits or measurements not collected and/or recorded will be considered deviations unless otherwise specified. The Principal Investigator or authorized designee(s) must ensure the accuracy and completeness of the recorded data and then provide his/her electronic signature on the Club Hernie Registry Database (CNIL – Commission Nationale de l’Informatique et des Libertés – approved database). Each Principal Investigator or authorized designee(s) will be trained on the use of the Club Hernie database. Club Hernie does not have the capability to maintain an audit trail, data trail and edit trail; this is a deviation from ISO 14155:2020. All data (new, updated, previously entered) will be reviewed by sponsor with each Club Hernie database extraction. Data accuracy will be assessed by source data verification during monitoring visits. Prior to study closure each Principle Investigator will approve their final set of study data.

Data entered must be traceable to source documents. Source documentation is defined as the first time data appear, and may include original documents, data, and records (e.g., hospital records, clinical and office charts, procedure reports, laboratory notes, memoranda or evaluation checklists, pharmacy dispensing records, copies or transcriptions certified after verification as being accurate copies, microfiches, photographic negatives, microfilm or magnetic media, X-rays, subject files, device data and records kept at the pharmacy, at the laboratories and at medico-technical departments involved in the study).

In general, CRFs may not serve as source documents. The data reported on the CRFs and into Club Hernie shall be derived from and consistent with source documents, and any discrepancies shall be explained in writing by the site staff. If data elements are not documented in the medical record, but are required for CRFs or Club Hernie an exception may be made (e.g., the completion of QoL Questionnaires, clinical scales, Inclusion CFRs, Study Exit CFRs, Protocol Deficiency CRFs, Device Deficiency CRFs, and Adverse Event CRFs). Source documentation for data elements not routinely captured in medical records may vary from study site to study site; the study site may use source document worksheets if identified as source documents.

The investigator must ensure the availability of source documents from which the information on the CRFs or Club Hernie entry was derived. The type and location of source documents should be documented. Where printouts of electronic medical records, are provided as source documents, or where copies of

source documents are retained as source documents, those should be certified. Certification must contain (1) the signature of the individual making the copy, (2) the date the copy was made and (3) a statement attesting to the accuracy and completeness of the copy.

## **11.12 Deviation Handling**

A study deviation is defined as an event within a study that did not occur according to the CIP or the CTA. Prior approval by Medtronic is expected in situations where the investigator anticipates, contemplates, or makes a conscious decision to deviate. The investigator is not allowed to deviate from the CIP, except under emergency circumstances to protect the rights, safety and well-being of human subjects. Prior approval is not required when a deviation is necessary to protect the safety, rights or well-being of a subject in an emergency or in unforeseen situations beyond the investigator's control (e.g. subject failure to attend scheduled follow-up visits, inadvertent loss of data due to computer malfunction, inability to perform required procedures due to subject illness).

For medically justifiable conditions which preempt a subject's ability to complete a study-required procedure, it may be permitted to report only one deviation which will apply to all visits going forward. This may also apply for other unforeseen situations (e.g. the subject permanently refuses to complete a study required procedure and the data will not contribute to the primary end point analysis). However, prior approval from Medtronic is required for such situations.

All study deviations must be reported on the CRF regardless of whether medically justifiable, pre-approved by Medtronic, an inadvertent occurrence, or taken to protect the subject in an emergency. Multiple deviations of the same type at the same visit may be reported on one case report form.

In the event the deviation involves a failure to obtain a subject's consent, or is made to protect the life or physical well-being of a subject in an emergency, the deviation must be reported to the EC as well as Medtronic within five (5) working days. Reporting of all other study deviations should comply with EC policies and/or local laws and must be reported to Medtronic as soon as possible upon the study site becoming aware of the deviation. Reporting of deviations must comply with EC policies, local laws, and/or RA requirements.

Medtronic is responsible for analyzing deviations, assessing their significance, and identifying any additional corrective and/or preventive actions (e.g. amend the CIP, conduct additional training, terminate the investigation). Repetitive or serious investigator compliance issues may result in initiation of a corrective or preventative action plan with the investigator and study site, and in some cases, may necessitate suspending enrollment until the problem is resolved or ultimately terminating the investigator's participation in the study. Medtronic will provide study site-specific reports to investigators summarizing information on deviations that occurred at the investigational study site on a periodic basis.

Examples of study deviations include but are not limited to:

- Failure to obtain proper IC
- Failure to collect required study data (e.g. required abdominal CT scan)
- Required study data collected outside of visit window
- Inclusion/exclusion criteria not met

## **11.13 Subject Exit, Withdrawal or Discontinuation**

### **11.13.1 Study Exit**

A study exit CRF is required for all subjects. Prior to exiting a subject from the study, it is recommended to follow the subject until all ongoing system and/or procedure related AEs are resolved or unresolved with no further actions planned. Following exit, subjects will continue to receive standard medical care. Upon exiting from the study, no further study data will be collected or study visits will occur for the subject. All data available through the time of the subject's exit will be used for analysis.

Subjects are urged to remain in the study as long as possible but may be exited from the study for any of the following situations:

- Study completed
- Subject lost to follow-up
- Subject death
- Subject chooses to withdraw (e.g., consent withdrawal)
- Investigator deems withdrawal necessary (e.g., medically justified, inclusion/exclusion criteria not met, failure of subject to maintain adequate study compliance)
- Mesh removal

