### 10.2. Subject Enrollment

A subject is considered enrolled in the study when it is confirmed they meet all pre-operative inclusion and no exclusion criteria, the ICF is signed and they have been implanted with the device. A subject must be followed for the full 24 months if the procedure was begun or completed with the study device. No study procedures, or data collection will be performed until informed consent form has been completed.

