### **11.13.2 Screen Failure**

Subjects who provide study consent, but then are determined to be ineligible will be considered a screen failure and will not require additional study follow-up visits. The reason for the screening failure will be clearly recorded in the applicable POETRY Study Exit Form.

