### **11.13.4 Withdrawal**

The reason for study exit will be documented on the POETRY Study Exit form and Club Hernie Registry Database. A subject can withdraw from the study at any time. In the event the subject withdraws consent during the study, the date and reason for withdrawal (if known) will be documented. If the study Investigator voluntarily removes a subject from further study participation, supporting documentation

must be in place for the rationale and date of removal. Follow up of subjects withdrawn will be determined by investigator. Withdrawn subjects will not be replaced.

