## 15.5 Analysis Sets

- The Performance Analysis Set (PAS) includes all enrolled subjects excluding subjects who became pregnant during the follow-up, or subjects who undergo unscheduled abdominal surgery during study follow-up, which may increase the risk and cause of incisional hernia occurrence\*.

\*Subject follow-up data, starting from the event's occurrence, will be excluded/remove from the performance analysis.

- Per Protocol Analysis Set (PPAS) is a subset of PAS excluding subjects with protocol violation and major protocol deviation(s) that may impact the primary endpoint assessment. More precisely, reason for exclusion may include but is not limited to,
  - Patient wrongly included (*i.e.* patient was enrolled but does not meet all the eligibility criteria).
  - Failure to obtain informed consent.
  - Deviation resulting from device use outside the recommended use in the IFU.
  - Patient who receives the incorrect device or device is misused
- Safety Analysis Set includes all enrolled subjects.

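### Protocol 11.13.1 lets the investigator end follow-up of an implanted subject for ineligibility or poor compliance, in conflict with the 24-month rule in 10.2 and with the analysis sets

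*Protocol*

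**What the plan says.** Four parts of the plan bear on an implanted subject who turns out to be ineligible or who complies poorly.

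- **Follow-up duty.** Protocol 10.2: "A subject must be followed for the full 24 months if the procedure was begun or completed with the study device". It states no exception. The same section makes implantation part of the definition of enrolment.
- **Exit.** Protocol 11.13.1 allows exit where "Investigator deems withdrawal necessary (e.g., medically justified, inclusion/exclusion criteria not met, failure of subject to maintain adequate study compliance" applies. The consequence is "Upon exiting from the study, no further study data will be collected or study visits will occur for the subject", with the proviso "All data available through the time of the subject's exit will be used for analysis". Section 11.13.4 adds: "Follow up of subjects withdrawn will be determined by investigator".
- **Analysis sets.** Protocol 15.5 and SAP 7.1.3 build the Performance Analysis Set (PAS) and the Safety Analysis Set from all enrolled subjects. Ineligibility is a reason to leave only the Per Protocol Analysis Set (PPAS): "Patient wrongly included (*i.e.* patient was enrolled but does not meet all the eligibility criteria".
- **Deviations.** Protocol 11.12 gives unmet eligibility criteria and a missing CT as examples of study deviations, to be reported on the CRF.

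Protocol 15.1 and SAP 7.4 analyse available data without imputation. Protocol Table 2 places the first abdominal CT at 12 months.

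**The concern.** A site that finds an implanted subject ineligible has two incompatible instructions: follow to 24 months under 10.2, or exit under 11.13.1 and collect nothing more. The case is foreseeable. Exclusion 2c (contaminated or infected field) is assessed during surgery, and a third high-risk factor (exclusion 8) can surface on later chart review. Poor compliance is by its nature mostly a follow-up event.

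The choice rests with an investigator who is not blinded (Protocol 10.1). The primary test has no control arm in which similar losses could offset these, and nothing is imputed. A subject exited before 12 months has no CT-based hernia outcome, and the 24-month adverse event record is cut short. The 20% attrition allowance replaces numbers. It gives no protection if exit is related to hernia risk.

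**Working it through.** **1. The rules applied to one case.** The mesh is in place and the subject is then found not to meet a criterion.

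- 10.2: visits, examination and CT continue to 24 months.
- 15.5 and SAP 7.1.3: the subject is in the PAS and the safety set, so the primary test expects an outcome.
- 11.12: the finding is a reportable deviation.
- 11.13.1: the investigator may exit the subject, and no outcome follows.

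The first three are consistent with each other. The fourth is not consistent with the first two. For compliance there is a further mismatch: 11.13.5 asks for repeated documented contact attempts after each missed visit and does not count anyone as lost until the end of the study, while 11.13.1 lets the same subject be exited.

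**2. The plan's own figure.** Inputs from Protocol 15.6: 10% against 20%, 80% power, two-sided 5%.

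n = [(1.960 × √(0.2 × 0.8) + 0.842 × √(0.1 × 0.9)) / 0.1]² = [(0.784 + 0.252) / 0.1]² = 107.43, rounded up to 108; 108 / 0.80 = 135.

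Both stated figures reproduce, and neither depends on this point. By the exact binomial at n = 108 (lower tail at most 0.025), the test succeeds with 13 or fewer hernias. The tail probability is 2.1% if the true rate is 20%, and the power is 81.0% if it is 10%.

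**3. A few exits.** The number exited (e) and their hernia rate (q) are assumptions; the documents give neither. With a true rate of 20% in all 108, the rate among retained subjects is r = (21.6 − e × q) / (108 − e).

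| e | q | r | success limit | chance of false success | same n, no selection |
|---|---|---|---|---|---|
| 0 | – | 20.0% | 13 of 108 | 2.1% | 2.1% |
| 5 | 30% | 20.1/103 = 19.5% | 12 of 103 | 2.4% | 1.8% |
| 8 | 30% | 19.2/100 = 19.2% | 11 of 100 | 2.0% | 1.3% |

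The last column shows that part of the movement comes only from the discreteness of the test.

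**4. Many exits.** Start from 135 implanted and lose a share w with hernia rate q: r = (0.20 − w × q) / (1 − w).

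| w | q | r | chance of false success |
|---|---|---|---|
| 5% | 30% | 19.5% | 2.5% |
| 10% | 40% | 17.8% | 6.7% |
| 20% | 30% | 17.5% | 8.1% |
| 20% | 40% | 15.0% | 23.8% |
| 20% | 20% | 20.0% | 2.1% |

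The large values need the whole attrition allowance to consist of risk-related exits. If exit is unrelated to risk there is no bias.

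**5. A borderline result.** Exact two-sided p against 20%: 13/108 gives 0.040 and 14/108 gives 0.071. Starting from 14/108, exit of three subjects of whom two would have had hernias gives 12/105, p = 0.028. With one of the three it is 13/105, p = 0.051. Exit of a single subject who would have had a hernia gives 13/107, p = 0.040. A reversal is possible at that exact count, but it depends on where the result falls.

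**The case against.** Section 10.2 cannot be absolute. Death, withdrawal of consent and mesh removal also end follow-up, and Protocol section 7 refers the reader to 11.13 for exit rules, so 11.13 can be read as the list of exceptions. Investigator removal needs a documented reason and date (11.13.4), subjects are urged to stay in, and the sponsor reviews deviations. This explains most of the exit list. It does not explain the two reasons at issue: they are discretionary, and the analysis sets are written as if these subjects still supply outcomes.

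Three stronger readings are tempting, and the documents do not support them.

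- *Implanted subjects can be relabelled as screen failures.* Section 11.13.2 has no time limit: "Subjects who provide study consent, but then are determined to be ineligible will be considered a screen failure and will not require additional study follow-up". In context it most likely concerns the time before implantation. Eligibility is reconfirmed on the day of surgery (Table 2, note 1), SAP 7.1.1 counts screen failures and enrolled subjects separately, and 15.5 calls a wrongly included patient enrolled.
- *Exited subjects vanish from the data.* Data up to exit are used, so a hernia already found is kept. The subject stays in the safety set. Section 13.3 asks for up to 30 days of follow-up of unresolved system- or procedure-related events, and 13.5 has device-related events monitored to resolution where possible.
- *The exits favour the device.* Several exclusions do pick out subjects likely to be at higher risk (more than 2 high-risk or more than 5 total factors, a contaminated field, an existing ventral hernia). But inclusion criterion 4 also makes a subject with too few risk factors ineligible, and nothing in the documents links poor compliance to hernia.

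**Conclusion.** The conflict is real and follows from the text alone: 11.13.1 against 10.2, and against 15.5 with SAP 7.1.3. Its effect is truncated follow-up and missing 12- and 24-month CT outcomes at the investigator's discretion, in a single-arm test with no imputation. It is not deletion from the analysis sets.

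Neither the direction nor the size of any bias can be stated, because the documents give no expected number of such exits and no hernia rate for them. Under the assumptions in the first table the effect on false success is very small. It becomes material only if exits are numerous and strongly related to risk. A reader might infer from the borderline example that the rule is likely to overturn the trial's conclusion; that needs a result of exactly 14/108 or similar and a particular set of exits. The sample size of 108 evaluable and 135 enrolled is unaffected. The amendment is justified because the rules disagree and outcomes that were never collected can afterwards only be bounded by sensitivity analysis, not recovered.

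**What to change.** Reconcile the sections in a protocol amendment.

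- **11.13.1:** limit unmet eligibility criteria and inadequate compliance, as reasons for exit, to subjects not yet implanted.
- **Same section:** state that implanted subjects found ineligible or poorly compliant are reported as deviations (already required by 11.12) and stay in scheduled follow-up to 24 months unless they withdraw consent or another listed exit reason applies. State that ineligible subjects are handled through the PPAS.
- **11.13.4:** for implanted subjects, refer to 10.2 in place of follow-up at the investigator's choice.
- **11.13.2:** as a clarification only, add that screen failure applies before implantation of the study mesh.

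The sample size and the primary test do not change. The cost is a few sentences, plus the scheduled visits and CTs for the few subjects who would otherwise have been exited. For those whose CT is not standard of care, Protocol 12.1 puts the dose at about 8 mSv per scan. The schedule already includes these scans, but the amendment should acknowledge that exposure.

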### **11.13.2 Screen Failure**

Subjects who provide study consent, but then are determined to be ineligible will be considered a screen failure and will not require additional study follow-up visits. The reason for the screening failure will be clearly recorded in the applicable POETRY Study Exit Form.

### **11.13.3 Discontinuation**

Subjects who provide study consent, and are deemed eligible, but do not undergo the procedure with the study device will be considered “discontinued” and will be followed until discharge (no additional follow-up visits will be required). The reason for discontinuation will be clearly recorded in the applicable POETRY Study Exit Form and Club Hernie Registry Database.

### **11.13.4 Withdrawal**

The reason for study exit will be documented on the POETRY Study Exit form and Club Hernie Registry Database. A subject can withdraw from the study at any time. In the event the subject withdraws consent during the study, the date and reason for withdrawal (if known) will be documented. If the study Investigator voluntarily removes a subject from further study participation, supporting documentation

must be in place for the rationale and date of removal. Follow up of subjects withdrawn will be determined by investigator. Withdrawn subjects will not be replaced.

### **11.13.5 Lost to Follow-Up**

Attempts to reach the subject will be performed by the site after each missed follow-up visit. For each visit, the following should be performed;

- Three (3) phone calls should be made to the subject at various times and least a day apart. Each attempt should be clearly documented in the source documents and the response or lack thereof should be captured.
- If there is no response to the phone calls, then an official, certified letter should be written to the subject. A copy of the letter and return or delivery receipts should be retained in the subject's source document.

The subject will not be considered lost to follow-up until the end of the study. Four (4) failed documented attempts of meticulous postal reminders and phone calls for each visit will be used to minimize the non-response bias. Lost to Follow-up subjects will not be replaced.

### **11.13.6 Mesh Removal**

In the case that the study mesh is removed from the subject the subject will be exited from the study 30 day after mesh removal. The reason for study exit will be documented on the POETRY Study Exit form and the mesh shall be returned to the sponsor.

### **11.13.7 Study Completed**

At the completion of the 24-month follow-up visit, subjects will be exited from the study. The 24-month follow-up visit and exit visit should be combined, and both a 24-month follow-up CRF and a Study Exit CRF need to be completed.

---

## **12. Risks and Benefits**

### **12.1. Potential Risks**

Medtronic follows rigorous Quality Assurance and Control procedures throughout the life of a product, from the business analysis phase through development, market release, and post-market surveillance. For studies following ISO 14155, the risk analysis process for the ProGrip™ self-gripping polyester mesh is being performed in accordance with ISO 14971, and will ensure that the level of risk is acceptable prior to starting the study. The residual risks have been classified as acceptable in the worst cases.

Possible additional risks for participating in this study include the following (although others are possible): hematoma, seroma, adhesion, infection, fistula, chronic pain, inflammation, and recurrence, allergic

reaction to the components of the product and urinary retention (which may occur with the use of anesthetics). Details can be found in the device IFUs (Section 19.2).

For subjects that are operated for an oncologic colorectal procedure, the abdominal CT-Scan is part of standard of care. For other procedures, as a result of participation in this study, subjects may be exposed to radiation from x-ray procedures. In addition to the routine procedures, the x-ray exams used for this study include a CT scan evaluation of the abdominal cavity. These x-ray exams deliver up to a total radiation dose of approximately 8 mSv each, and subjects will undergo 1 CT scans at the 1 and 2 year post-operative visits. A milliSievert (mSv) is a unit of radiation dose. For comparison, the average person in France receives 2.9mSv each year from natural sources of radiation. A slight increase in cancer risk may exist for people exposed to radiation.

Following the fluoroscopic procedure, as with any X-ray exposure in everyday life, the skin area exposed to those x-rays could react to produce an effect similar to a sun burn. A skin reaction, if it occurs at all, could show up from a few hours to a few weeks after the procedure, and usually goes away on its own. If a skin reaction is found the subject should promptly report this to the study physician.

The mesh will not stretch to accommodate growth so it may be inappropriate to have a mesh implanted if the subject is planning a future pregnancy. A pregnancy after a laparotomy is a risk factor for developing an incisional hernia.

There may be additional risks related to this study that are not yet known.

